7.10.3 Remuneration

All participants enrolled onto the study will be remunerated for their time. Participants who fail to complete the study, for whatever reason, may claim a proportion of the remuneration commensurate with the extent of their participation. Taxi transfers will be arranged to/from the study site for all visits.

For participants who attend the consent/screening only no voucher will be offered. Pre-screening by telephone will be conducted to limit the number of instances where participants attend the site and are subsequently not enrolled (failure to meet eligibility criteria). Travel expenses incurred in order to attend the consent/screening visit will be paid upon request, and require the completion of a University of Sheffield claim form.

7.11 Definition of the end of trial

The end of the trial is defined as the point at which all lab analyses required for the study endpoints has been completed.

7.11.1 Early termination of the trial

The criteria for electively stopping the trial prematurely includes:

- New information becomes available on either of the study interventions or the study procedures that suggests that participants or researchers will be placed at unacceptable risk. This will be decided by the CI and Sponsor.
- The CI and Sponsor, with the support of the TMG, deems that nature and/or frequency of adverse events is inconsistent with expectations and suggests that participants are being placed at greater risk.

The decision to terminate may also occur because of a regulatory authority decision or a change in opinion of the REC.

8. TRIAL TREATMENTS

8.1 Name and description of investigational products

The treatments used in this study are listed in Table 9.1.

Table 8.1: Investigational products

Name, Strength & Form	Brand Name	Pack size and quantity per participant	Manufacturer	Formulation
Betamethasone Valerate 0.1% topical cream	Betnovate (0.1%) cream	1x 100g tube*	Glaxo Wellcome UK Limited.	Betamethasone Valerate BP 0.122%, Chlorocresol BP, Cetomacrogol 1000 BP, Cetostearyl Alcohol BP, White Soft Paraffin BP, Liquid Paraffin BP, Sodium Acid Phosphate BP, Phosphoric Acid BP, Sodium Hydroxide BP, Purified Water
Crisaborole 2% ointment	N/A	2x 60g tube	Pfizer	Crisaborole 2%, White Petrolatum, Propylene Glycol, Mono- And Di- Glycerides, Paraffin, Butylated Hydroxytoluene, And Eddate Calcium Disodium

*Additional tube can be prescribed upon request where usage tracks consistently high (noting upper acceptable usage limit of 112g)

8.2 Regulatory status of the drugs

8.2.1 *Betamethasone Valerate (0.1%) cream*

Betamethasone Valerate (0.1%) cream is currently licenced in the UK for the treatment of eczema and will be used in accordance with this licence in this study (see Betnovate [0.1%] cream SmPC). Betamethasone valerate creams are manufactured by a number of companies, however this trial will be performed using the Betnovate (Glaxo Wellcome UK Ltd) brand only to avoid the introduction of variability arising from the differences in topical formulation (known to affect bioavailability of the active).

8.2.2 *Crisaborole (2%) ointment*

Crisaborole (2%) ointment is not currently licenced in the UK; however, it is licenced by the FDA for use in the United States of America and will be used in accordance with this licence in this study.

8.3 Product characteristics

8.3.1 *Betamethasone Valerate (0.1%) cream*

Please refer to the attached SmPC

8.3.2 *Crisaborole (2%) ointment*

Please refer to the attached crisaborole Investigator's Brochure (IB)

8.4 Drug supply

8.4.1 *Betamethasone Valerate (0.1%) cream*

Betnovate (0.1%) cream will be provided as supplied by the manufacturer (no re-packaging). Whilst this product is marketed in the UK the Pharmacy does not stock this item (instead supplying from a range of generic manufacturers with varying formulations). The Pharmacy will therefore order the product as (segregated) clinical trial stock. Annex 13 compliant labels will be applied prior to dispensing by the pharmacy (example attached).

8.4.2 *Crisaborole (2%) ointment*

Crisaborole (2%) ointment will be provided by Pfizer. The product will be imported by Pfizer and released onto this study by a suitable Qualified Person nominated by Pfizer. The product will be provided in plain packaging with Annex 13 compliant labels (example attached).

8.5 Drug storage

The study pharmacist or other appropriately trained personnel, will ensure that all investigational products are stored in a secured area with controlled access under required storage conditions and in accordance with applicable regulatory requirements.

Investigational products should be stored in their original containers and in accordance with the labels. The conditions for storing both products are:

- Store at 15–25°C (59–86°F) for crisaborole (2%) ointment and ≤25°C (77°F) for betamethasone valerate (0.1%) cream.

Site systems must be capable of measuring and documenting (for example, via a log), at a minimum, daily minimum and maximum temperatures for all site storage locations (as applicable, including frozen, refrigerated, and/or room-temperature products). This should be captured from the time of investigational product receipt throughout the study. Even for continuous-monitoring systems, a log or site procedure that ensures active evaluation for excursions should be available. The intent is to ensure that the minimum and maximum temperature is checked each business day to confirm that no excursion occurred since the last evaluation and to provide the site with the capability to store or view the minimum/maximum temperature for all non-working days upon return to normal operations. The

operation of the temperature monitoring device and storage unit (for example, refrigerator), as applicable, should be regularly inspected to ensure they are maintained in working order.

Any excursions from the product label storage conditions should be reported to the CI upon discovery. The site should actively pursue options for returning the product to the storage conditions described in the labelling, as soon as possible. Deviations from the storage requirements, including any actions taken, must be documented. Permitted excursions require no further action.

Once an excursion outside the permitted range is identified, the investigational product must be quarantined and not used until the CI provides permission to use the investigational product. For crisaborole (2%) ointment the CI will seek permission from Pfizer to use the investigational product OR request replacement stock. It will not be considered a protocol deviation if Pfizer approves the use of the investigational product after the temperature excursion. Use of the investigational product prior to Pfizer approval will be considered a protocol deviation. Specific details regarding information the site should report for each excursion will be provided to the site. For betamethasone valerate (0.1%) cream, replacement stock will be procured, with the permission of the CI and where necessary the Funder, in the event of an excursion outside the permitted range.

Receipt of materials, door opening and closing, and other routine handling operations where the products are briefly out of the temperature range described in the labelling are not considered excursions. Site staff will instruct participants and/or parents/legal guardians on the proper storage requirements for take home investigational products (details can be found in the treatment diary).

8.6 Preparation and dispensing

The investigational products will be prescribed by a medically qualified and appropriately delegated member of the research team.

The investigational products will be labelled (as required) and dispensed by the Pharmacist, according to the randomization schedule, at the request of the site research facility. Annex 13 compliant labels will be used, containing study specific usage instructions including dose and application frequency, and capture the unique participant ID, the participant's initials and the 'application site' (according to the randomization).

Unblinded researchers at the site research facility, as delegated by the PI, will issue the investigational products to the study participants during visit 1, provide the demonstration of product application and undertake all compliance monitoring. Unblinded researchers will not be involved in the collection of study data.

8.7 Treatment regimen

Every enrolled participant will undergo the same intervention, which involves the use of 2 investigational products according to a predefined regimen (Table 8.2).

Table 8.2: Treatment conditions

Treatment site	Investigational Product
Right/left forearm	Betamethasone Valerate (0.1%) cream
Right/left forearm	Crisaborole (2%) ointment

Twice-daily self-administered application of 1 finger-tip units of either crisaborole (2%) ointment or betamethasone valerate (0.1%) cream to the designated treatment areas on the volar side of the respective forearm for 28 days. The 2 daily applications should be conducted once in the morning and once in the evening, separated by at least 6 hours. When washing, the product should be applied after washing (not before). Randomized site allocation to avoid site dependent effects.

Participant diaries will be provided to record product usage (compliance) and provide usage instructions, including a visual guide to the IP allocation.

8.8 Prior and concomitant medication

All prior medications, including all medications, non-medication therapies, bland (non-medicated) emollients, over the counter drugs, vitamins, and antacids used within 28 days prior to Screening will be recorded. Any changes in concomitant medications or dosage will be recorded at Baseline/Day 1 and at each subsequent visit until completion (defined as completion of the last study visit). Medication entries should provide the correctly spelled drug or therapy name and the dose, units, frequency, route of administration, start and stop date, and reason for use. The use of any concomitant medication must relate to the participant's medical history or to an AE, except for vitamins/nutritional supplements and routine immunizations.

8.8.1 Prohibited Medications

Classes of medications and non-medication therapies that may alter the underlying (inflammatory) state of the skin and for which washout is required prior to Baseline/Day 1 are listed below. If a participant requires a washout, the investigator or his/her designee will provide instructions on discontinuing the prohibited medication(s) or non-medication therapy at the Screening Visit. The use of any excluded medications during the study will result in discontinuation of the participant.

- Medications Prohibited 12 weeks prior to Baseline/Day 1 and throughout the study
 - Biological drugs.
- Medications Prohibited 28 Days Prior to Baseline/Day 1 and throughout the study
 - Use of systemic (oral, parenteral) corticosteroids. Inhaled glucocorticoids of low to moderate doses for treatment of asthma are allowed.
 - Use of systemic immunosuppressive agents, including but not limited to, methotrexate, cyclosporin, azathioprine, hydroxychloroquine, and mycophenolate mofetil.
 - Light therapy Ultraviolet (UV), Ultraviolet B (UV-B), psoralen–UV-A [PUVA]) anywhere on the body.

- Use of TCS, or TCI *on the test areas*.
- Medications Prohibited 14 Days Prior to Baseline/Day 1 and throughout the study
 - Use of systemic antibiotics.
 - Use of TCS, or TCI, anywhere on the body.
 - Use of crisaborole ointment, 2%, anywhere on the body.
 - Use of topical retinoids or benzoyl peroxide *on the test areas*.
 - Use of topical antihistamines *on the test areas*.
- Medications Prohibited 7 Days Prior to Baseline/Day 1 and throughout the study
 - High doses of systemic sedating antihistamines (eg, hydroxyzine or diphenhydramine or other sedating antihistamines). Use of over-the-counter systemic sedating and non-sedating antihistamines is permitted at recommended doses for allergic rhinitis/hay fever
 - Use of bland (non-medicated) emollients, moisturisers or sunscreen *on the test areas*, within 7 days prior to Baseline/Day 1. Use of bland (non-medicated) emollient(s) and/or sunscreen is permitted during the study to manage dry skin and sun exposure in areas surrounding but not on or overlapping the test areas.
- Medications prohibited from Baseline/Day 1 and throughout the study
 - Use of nonsteroidal anti-inflammatory agents (NSAID's, excludes paracetamol), including ibuprofen, naproxen, diclofenac, celecoxib, mefenamic acid, etoricoxib, indomethacin, high-dose aspirin.
 - Use of vasoactive drugs in a non-stable (eg, escalating or decreasing, or as needed) regimen including: metaraminol, adrenaline/epinephrine, noradrenaline/norepinephrine, phenylephrine, dobutamine, dopamine, dopexamine, oxymetazoline.

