7.4 Study visits

Procedures conducted during the study visits will be recorded using paper CRFs first (and then transferred to the EDC) or directly using an electronic form in the EDC system (which double as task lists for each visit). Where direct electronic entry is used, at the end of each session the database entry

will be printed and signed by the researcher to verify the source data and stored in the site file. Further details can be found in section “Study Conduct”.

At the start of every visit consent will be reconfirmed and enquiries will be made about potential AE and concomitant medication (AE and Concomitant Medication forms will be completed as required).

A description of the visits is provided below:

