7.4.9 Visit 8, Day 57 +/- 4 days (approx. 2.5 hours)

- Re-confirm verbal ascent to continue the study
- Capture adverse events and new concomitant medications
- Transfer participant to skin barrier suite
- Participants will need to acclimatize the skin on their forearms to the room conditions for 20 minutes.
- The measurement sites should be marked out on each arm using a marker pen (as discreetly as possible). The marker is easily removed by washing the skin at the end of the study visit. Hair interferes with the measurements, so where present we may need to trim it.

- Once acclimatised the condition of the skin should be assessed:
 - Visually score skin dryness and redness/erythema at each treatment area
 - Capture 2D skin images of the test areas of skin
 - Perform Mexameter measurements of objective skin redness at each site
 - Take OCT (structural & angiographic) images/scans with the Vivosight at each test site
 - Measure TEWL at each test site
 - Collect FTIR spectra at each test site
- Ask participants to complete a claim form for the remuneration

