7.10.2 Participant withdrawal

When an individual who has signed the Informed Consent Form is not enrolled in the study or withdraws/is withdrawn prior to completing the study, the reason is to be documented on the Participant Screening, Enrolment & Completion Log. Reasons for participant withdrawal may include:

1. Participant is determined to be ineligible after enrolment
2. Participant's choice to withdraw
3. Exclusion criteria met
4. Non-compliance with the study protocol.
5. Adverse event, including a relapse of AD (defined as an escalation in treatment, i.e. the need for topical corticosteroids).
6. Loss-to-follow (participant cannot be contacted)
7. Other

Participants may withdraw from the study at any time at their request, or they may be withdrawn at any time at the discretion of the PI, or designee for safety, behavioural, or administrative reasons. If a participant does not return for a scheduled visit, at least 2 attempts will be made to contact the participant in order to establish the reason for withdrawal, and the outcome will be documented, if reasonably possible within the constraints of the study design. No more than 4 attempts will be made to contact participants; a voicemail to a personal mobile number may be left once but this will not detail any study or clinical information, it will be limited to a request to call back on a given number. The PI or designee should inquire about the reason for withdrawal, request that the participant return

for a final visit, if applicable (if withdrawing from the study during the treatment period between study visits), and follow-up with the participant regarding any unresolved adverse events. In such circumstances, where the treatment regimen has not completed the final visit will be conducted solely to retrieve the products and capture any unreported AE's.

Additional participants may be enrolled in the study, up to the maximum recruitment target, to compensate for early participant withdrawal.

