8.11 Compliance monitoring

The IP will be weighed at every visit and the diary reviewed. Both product weights and product application information will be captured in the EDC system.

Visits 2-5 are conducted for the purposes of compliance monitoring and participant training only. The aim is for participants to undertake 5 supervised applications during the first 2 weeks of treatment (including at the end of visit 1) to monitor compliance and encourage consistent adherence to the application regimen. To minimize the burden on participants sufficient variance has been included to allow gaps of up to 7 days between supervised applications. It is anticipated that after 5 observed applications during the first 2 weeks, participants will be sufficiently trained to reliably carry out the treatment. Compliance visits are not expected to take place on weekends. Only one application per day is to be supervised. The sessions should be arranged such that participants can fully adhere to the treatment regimen, requiring 2 applications per day, once in the morning and once in the afternoon/evening separated by at least 6 hours.

Treatment usage should be determined from the IMP weights during every visit so that the information can be shared with the participant (and recorded in the treatment diary) in the context of expected usage, and any required changes in dosage or application technique suggested prior to the supervised application. Supervised applications should be performed at every study visit (after any scheduled skin assessments) to ensure consistent adherence to the dosing regimen. Re-training should be provided as required based on completion of the diary, product weights and application technique. The criteria for assessing usage is provided in the next section.

The diary should be reviewed at every visit for completeness and any gaps in application discussed with the participant. If, at all study visits except visit 1-5, the participant is found to have missed more than 20% of the scheduled applications, and/or missed more than 4 consecutive applications, and/or missed either of the 2 applications immediately preceding a study visit involving skin assessments the participant should be withdrawn. During Visits 1-5 the study Investigators may use their discretion to judge a participant's ability to adhere to the treatment regimen.

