8.13 Investigator termination of participant involvement

Examples of participant non-compliance that may arise are:

- The participant fails to satisfactorily follow the study schedule (appointments not attended within the given timeframes), as per the schedule of events and this affects collection of data pertaining to the primary outcome measures.
- The participant fails to apply the product at the specified times/days. Participants who miss more than 20% of the scheduled applications, and/or miss more than 4 consecutive applications, and/or miss either of the 2 applications immediately preceding a study appointment should be withdrawn.
- The participant fails to use the investigational products in acceptable quantities (see "treatment dosing and compliance"). At each session usage should be assessed. Where IP use is above or below expectations a new demonstration should be provided. Supervised applications are performed at every visit as required.
- The participant fails to bring the diary to any visit and cannot provide their usage history. Where a diary is not available, the participant should be asked to recite their application history for the given study period and bring the diary at the next visit. Every effort should be

made to retrieve the diaries. Where completed diaries cannot be obtained *AND* a participant's application history cannot be documented the participant should be withdrawn.

- The participant fails to bring the IP to study visits. If the participant fails to bring the IP to any visit they should be asked to return as soon as possible with the IP for weighing. A weight post 4-weeks treatment is required for compliance purposes (it is desirable for all other visits).
- Participants who inadvertently use the IP in the morning before the study visit – In these cases a new appointment should be scheduled where possible – if this is not possible within the constraints of the study the participant should be withdrawn.

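### Protocol 8.8.1 discontinues a participant for excluded-medication use even in the day 29 to 57 washout, and nothing provides for that participant's day-57 recovery measurement

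*Protocol*

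**What the plan says.** **Medication rule.** Protocol 8.8.1 lists prohibited medications, each banned for the whole study. The list includes TCS anywhere on the body, systemic antibiotics and NSAIDs. The consequence is stated without exception: "The use of any excluded medications during the study will result in discontinuation of the participant". Section 8.8 records medication changes up to the last study visit.

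**When use comes to light.** Section 7.4: "At the start of every visit consent will be reconfirmed and enquiries will be made about potential AE and concomitant medication". In 7.4.9 (Visit 8, day 57), the item "Capture adverse events and new concomitant medications" is listed before the transfer to the skin barrier suite and the scans. Table 7.1 schedules no visit between Visit 7 (day 29) and Visit 8.

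**Other withdrawal routes.** Section 7.10.2 gives reasons that may apply, among them "Non-compliance with the study protocol" and "Adverse event, including a relapse of AD (defined as an escalation in treatment, i.e. the need for topical corticosteroids)". On missed applications, 8.11 ends: "missed either of the 2 applications immediately preceding a study visit involving skin assessments the participant should be withdrawn". Section 8.13 says participants who "miss either of the 2 applications immediately preceding a study appointment should be withdrawn". Both sections also list missing more than 20% of applications, or more than 4 in a row. Section 8.11 applies at all visits except 1 to 5. At Visit 7 (7.4.8) the diary check is listed after the scans.

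**After withdrawal.** Section 7.10.2 offers a return visit to those who withdraw during the treatment period, and "where the treatment regimen has not completed the final visit will be conducted solely to retrieve the products and capture any unreported AE's". It provides no measurement visit for someone withdrawn later. SAP 2.4 starts the final analysis when every participant has either had the day-57 assessment or discontinued.

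**Use of day 57.** Protocol section 5 gives recovery towards baseline as the reason for the washout. SAP 6.2 lists day 57 minus day 29 epidermal thickness as a secondary endpoint.

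**The concern.** After day 29 the participant has handed back both products. Discontinuation can no longer mean stopping study treatment; it can only mean leaving the study. The rule then protects no treatment period and puts at risk the one measurement the washout exists to obtain. Use during the washout would most naturally surface at the start of Visit 8, with the participant present and the scans still to be done.

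At stake are the day-57 values of epidermal thickness, TEWL, redness and dryness (secondary) and of angiographic OCT and surface FTIR (exploratory). The loss may not be random. A flare treated with TCS triggers discontinuation, so missingness can depend on the state of the skin. A mixed model that holds days 15 and 29 cannot correct for a flare that happened later and was never measured. A value that is measured and flagged can be set aside in analysis; one never taken cannot be restored.

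**Working it through.** **Reading the text**

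1. Does 8.8.1 reach the washout? Yes. The bans cover the whole study, 8.8 records medication to the last visit, and no exemption follows day 29.
2. Does any section restore the day-57 measurement? None was found. The 7.10.2 return visit is for withdrawal during treatment. The discretion given to the principal investigator in 6.4 covers only tanning beds and leave-on products on the test areas.
3. Relapse: 7.10.2 is permissive. Relapse becomes binding only through 8.8.1, once TCS is actually used.
4. Missed applications: no doses are due after day 29. This route matters only when a threshold is first found to be crossed at the Visit 7 diary check, after the scans. The same check takes place at Visit 6 and Visit 6a (day 22), and a dosing-conditions check precedes the Visit 7 scans. Few cases remain.

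**The plan's sample size**

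Inputs (Protocol 10.1): difference 3.55 µm, SD 5 µm, two-sided 5%, power 80%, parallel groups. The t-test calculation gives 32.13, so 33 per group, as stated. 33/0.9 = 36.7, so 37 recruited, as stated. The primary endpoint is at day 29, so this point does not alter those figures.

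**Precision lost at day 57**

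SAP 7.2 model: change from day 1 on treatment, timepoint, their interaction and baseline, with a random subject effect. The subject effect cancels between arms. With residual variance s², the between-arm contrast of day 57 minus day 29 has

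variance = 2s²(1/n57 + 1/n29).

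With no loss, n57 = n29, so

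relative CI width = √[(1/n57 + 1/n29) / (2/n29)] = √[(n29/n57 + 1)/2].

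| n29 | n57 | (n29/n57 + 1)/2 | CI wider by |
|---|---|---|---|
| 33 | 32 | 1.0156 | 0.8% |
| 33 | 31 | 1.0323 | 1.6% |
| 33 | 29 | 1.0690 | 3.4% |
| 37 | 36 | 1.0139 | 0.7% |
| 37 | 35 | 1.0286 | 1.4% |
| 37 | 33 | 1.0606 | 3.0% |

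Generalised least squares on the full design with a baseline covariate gives the same values when the subject share of variance is set at 0.2 or 0.5 (assumed).

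Two departures make the loss somewhat larger:

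- If each arm's change is also correlated over time (assumed: 30% of variance arm-specific, 30% subject), the values for 33 become 1.0%, 2.1% and 4.4%.
- SAP 7.2 allows a fallback that analyses day 29 to 57 separately. A participant without day 57 then contributes nothing to it and the ratio is √(n29/n57). For 4 losses this is √(33/29) = 1.067 or √(37/33) = 1.059, that is 6.7% or 5.9%.

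**Possible shift from informative loss (illustration only)**

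If m of 37 are lost and their between-arm recovery contrast differs from that of the others by δ, the observed mean moves by (m/37)·δ. With δ = 2.5 µm (assumed): m = 2 gives 0.14 µm, m = 4 gives 0.27 µm, m = 7 gives 0.47 µm. The documents supply neither m nor δ.

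**The case against.** **No sentence forbids measuring.** The only explicit limit on a final visit applies when treatment is incomplete, and after day 29 it is complete. Section 7.4.9 runs from the medication enquiry to the scans with no stop instruction, so staff might record the use and carry on. This stands in part: the loss is inferred from mandatory discontinuation plus the absence of any retained follow-up. But staff who measured anyway would be acting against the plain sense of 8.8.1, and the outcome should not depend on which section they follow.

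**The other routes are weak.** A reader might infer that relapse or missed doses also end participation automatically. The text does not support that: 7.10.2 says reasons may include relapse, and 8.11 and 8.13 say should. The objection stands, and those routes are secondary here.

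**The rule has a rationale.** Section 8.8.1 targets products that may alter the inflammatory state of the skin, and a day-57 value taken after TCS on a test area does not show unassisted recovery. This stands for skin-active use on a test area, and it is a reason not to insist that such values form the main estimate. It is much weaker for an antibiotic, an NSAID or TCS on another part of the body.

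**Little is shown to follow.** Both forearms are lost together, so the between-arm contrast is biased only if loss relates to a difference in recovery between them, and nothing in the documents shows that. SAP 7.2 tests day 29 to 57 only if day 29 is significant and treats the secondary analyses as exploratory. The 37 recruited already allow for 4 losses. All of this stands and limits the severity; it does not justify discarding a measurement that is already scheduled.

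**Conclusion.** The point holds as a minor one. Section 8.8.1 requires discontinuation for excluded-medication use in the washout, when there is no treatment left to stop, and no provision keeps the day-57 measurement. Under the SAP's model the interval for the day 29 to 57 contrast widens by about 0.7% to 3.4% for 1 to 4 losses, and by up to 6.7% under the SAP's fallback analysis. The substantive issue is possibly informative missing data, of unknown amount and direction.

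This rests on reading discontinuation as leaving the study, which is the only meaning left after day 29, and on assumed numbers of losses, since the documents give no event rates.

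A reader might infer that the primary result is at risk. It is not: the cases considered here arise, or are found, after the day-29 scans.

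**What to change.** 1. In 8.8.1, state that once the day-29 assessments are done, excluded-medication use, AD relapse or missed applications are logged as deviations or intercurrent events. The participant is still asked to attend Visit 8 and be measured unless consent is withdrawn. Cross-refer in 7.10.2, 8.11 and 8.13.
2. For each topical medication entry, record whether the product was used on a test area.
3. In the SAP, report day-57 results with and without values taken after skin-active medication on a test area, or after systemic anti-inflammatory, immunosuppressant, biologic or phototherapy use. Choose the main estimate at the blind review already planned in SAP section 5.

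The prohibited list and clinical care stay as they are.

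**Cost:** a sentence or cross-reference in four protocol sections, one site note and one additional SAP analysis. Visit 8 is already scheduled and medication is already recorded up to it. The downside is that a few day-57 values will reflect other medication, which the paired reporting makes visible.
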